#### **8.4.4. Regulatory Reporting Requirements for SAEs**

Prompt notification by the investigator to the sponsor of an SAE is essential so that legal obligations and ethical responsibilities toward the safety of participants and the safety of a study intervention under clinical investigation are met.

The sponsor has a legal responsibility to notify both the local regulatory authority and other regulatory agencies about the safety of a study intervention under clinical investigation. The sponsor will comply with country-specific regulatory requirements relating to safety reporting to the regulatory authority, IRBs/ECs, and investigators.

Investigator safety reports must be prepared for SUSARs according to local regulatory requirements and sponsor policy and forwarded to investigators as necessary.

An investigator who receives SUSARs or other specific safety information (eg, summary or listing of SAEs) from the sponsor will review and then file it along with the SRSD(s) for the study and will notify the IRB/EC, if appropriate according to local requirements.

#### **8.4.5. Environmental Exposure, Exposure During Pregnancy or Breastfeeding, and Occupational Exposure**

Environmental exposure occurs when a person not enrolled in the study as a participant receives unplanned direct contact with or exposure to the study intervention. Such exposure may or may not lead to the occurrence of an AE or SAE. Persons at risk for environmental exposure include healthcare providers, family members, and others who may be exposed. An environmental exposure may include EDP, EDB, and occupational exposure.

Any such exposures to the study intervention under study are reportable to Pfizer Safety within 24 hours of investigator awareness.

##### **8.4.5.1. Exposure During Pregnancy**

An EDP occurs if:

- A female participant is found to be pregnant while receiving or after discontinuing study intervention.
- A female nonparticipant is found to be pregnant while being exposed or having been exposed to study intervention because of environmental exposure. Below are examples of environmental EDP:
  - A female family member or healthcare provider reports that she is pregnant after having been exposed to the study intervention by ingestion, or skin contact.

The investigator must report EDP to Pfizer Safety within 24 hours of the investigator's awareness, irrespective of whether an SAE has occurred. The initial information submitted should include the anticipated date of delivery (see below for information related to termination of pregnancy).

- If EDP occurs in a participant, the investigator must report this information to Pfizer Safety on the CT SAE Report Form and an EDP Supplemental Form, regardless of whether an SAE has occurred. Details of the pregnancy will be collected after the start of study intervention and until 28 days after the last dose.
- If EDP occurs in the setting of environmental exposure, the investigator must report information to Pfizer Safety using the CT SAE Report Form and EDP Supplemental Form. Since the exposure information does not pertain to the participant enrolled in the study, the information is not recorded on a CRF; however, a copy of the completed CT SAE Report Form is maintained in the investigator site file.

Follow-up is conducted to obtain general information on the pregnancy and its outcome for all EDP reports with an unknown outcome. The investigator will follow the pregnancy until completion (or until pregnancy termination) and notify Pfizer Safety of the outcome as a follow-up to the initial EDP Supplemental Form. In the case of a live birth, the structural integrity of the neonate can be assessed at the time of birth. In the event of a termination, the reason(s) for termination should be specified and, if clinically possible, the structural integrity of the terminated fetus should be assessed by gross visual inspection (unless pre-procedure test findings are conclusive for a congenital anomaly and the findings are reported).

Abnormal pregnancy outcomes are considered SAEs. If the outcome of the pregnancy meets the criteria for an SAE (ie, ectopic pregnancy, spontaneous abortion, intrauterine fetal demise, neonatal death, or congenital anomaly in a live-born baby, a terminated fetus, an intrauterine fetal demise, or a neonatal death), the investigator should follow the procedures for reporting SAEs. Additional information about pregnancy outcomes that are reported to Pfizer Safety as SAEs follows:

- Spontaneous abortion including miscarriage and missed abortion should be reported as an SAE;
- Neonatal deaths that occur within 1 month of birth should be reported, without regard to causality, as SAEs. In addition, infant deaths after 1 month should be reported as SAEs when the investigator assesses the infant death as related or possibly related to exposure to the study intervention.

Additional information regarding the EDP may be requested by the sponsor. Further follow-up of birth outcomes will be handled on a case-by-case basis (eg, follow-up on preterm infants to identify developmental delays). In the case of paternal exposure, the investigator will provide the participant with the Pregnant Partner Release of Information Form to deliver to his partner. The investigator must document in the source documents that the participant was given the Pregnant Partner Release of Information Form to provide to his partner.

#### **8.4.5.2. Exposure During Breastfeeding**

An EDB occurs if:

- A female participant is found to be breastfeeding while receiving or after discontinuing study intervention.
- A female nonparticipant is found to be breastfeeding while being exposed or having been exposed to study intervention (ie, environmental exposure). An example of environmental EDB is a female family member or healthcare provider who reports that she is breastfeeding after having been exposed to the study intervention by ingestion, inhalation, or skin contact.

The investigator must report EDB to Pfizer Safety within 24 hours of the investigator's awareness, irrespective of whether an SAE has occurred. The information must be reported using the CT SAE Report Form. When EDB occurs in the setting of environmental exposure, the exposure information does not pertain to the participant enrolled in the study, so the information is not recorded on a CRF. However, a copy of the completed CT SAE Report Form is maintained in the investigator site file.

An EDB report is not created when a Pfizer drug specifically approved for use in breastfeeding women (eg, vitamins) is administered in accordance with authorized use. However, if the infant experiences an SAE associated with such a drug, the SAE is reported together with the EDB.

#### **8.4.5.3. Occupational Exposure**

The investigator must report any instance of occupational exposure to Pfizer Safety within 24 hours of the investigator's awareness using the CT SAE Report Form regardless of whether there is an associated SAE. Since the information about the occupational exposure does not pertain to a participant enrolled in the study, the information is not recorded on a CRF; however, a copy of the completed CT SAE Report Form must be maintained in the investigator site file.

#### **8.4.6. Cardiovascular and Death Events**

Not applicable

#### **8.4.7. Disease-Related Events and/or Disease-Related Outcomes Not Qualifying as AEs or SAEs**

Not applicable

#### **8.4.8. Adverse Events of Special Interest**

Not applicable

##### **8.4.8.1. Lack of Efficacy**

This section is not applicable because efficacy is not expected in the study population.

#### **8.4.9. Medical Device Deficiencies**

Not applicable

#### **8.4.10. Medication Errors**

Medication errors may result from the administration or consumption of the study intervention by the wrong participant, or at the wrong time, or at the wrong dosage strength.

Medication errors are recorded and reported as follows:

Recorded on the Medication Error Page of the CRF	Recorded on the Adverse Event Page of the CRF	Reported on the CT SAE Report Form to Pfizer Safety Within 24 Hours of Awareness
All (regardless of whether associated with an AE)	Any AE or SAE associated with the medication error	Only if associated with an SAE

Medication errors include:

- Medication errors involving participant exposure to the study intervention;
- Potential medication errors or uses outside of what is foreseen in the protocol that do or do not involve the study participant.

Such medication errors occurring to a study participant are to be captured on the medication error page of the CRF, which is a specific version of the AE page.

Whether or not the medication error is accompanied by an AE, as determined by the investigator, the medication error is recorded on the medication error page of the CRF and, if applicable, any associated AE(s), serious and nonserious, are recorded on the AE page of the CRF.

In the event of a medication dosing error, the sponsor should be notified within 24 hours.

Medication errors should be reported to Pfizer Safety within 24 hours on a CT SAE Report Form **only when associated with an SAE**.

## 8.5. Pharmacokinetics

Blood samples of approximately 2 mL, to provide a minimum of 0.5 mL of plasma, will be collected for measurement of plasma concentrations of ritlecitinib as specified in the [SoA](#). Instructions for the collection and handling of biological samples will be provided in the laboratory manual or by the sponsor. The actual date and time (24-hour clock time) of each sample will be recorded.

The actual times may change, but the number of samples will remain the same. All efforts will be made to obtain the samples at the exact nominal time relative to dosing. Collection of samples up to and including 10 hours after dose administration that are obtained within 10% of the nominal time (eg, within 6 minutes of a 60-minute sample) relative to dosing will not be captured as a protocol deviation, as long as the exact time of the collection is noted on the source document and data collection tool (eg, CRF/DCT). Collection of samples more than 10 hours after dose administration that are obtained  $\leq$ 1 hour away from the nominal time relative to dosing will not be captured as a protocol deviation, as long as the exact time of the collection is noted on the source document and data collection tool (eg, CRF/DCT).

Samples will be used to evaluate the PK of ritlecitinib. Samples collected for analyses of ritlecitinib concentration may also be used to evaluate safety or efficacy aspects related to concerns arising during or after the study, or for other internal exploratory purposes.

Genetic analyses will not be performed on these plasma samples. Participant confidentiality will be maintained.

Samples collected for measurement of plasma concentrations of ritlecitinib will be analyzed using a validated analytical method in compliance with applicable SOPs.

The PK samples must be processed and shipped as indicated in the instructions provided to the investigator site to maintain sample integrity. Any deviations from the PK sample handling procedure (eg, sample collection and processing steps, interim storage or shipping conditions), including any actions taken, must be documented and reported to the sponsor. On a case-by-case basis, the sponsor may make a determination as to whether sample integrity has been compromised.

Any changes in the timing or addition of time points for any planned study assessments must be documented and approved by the relevant study team member and then archived in the sponsor and site study files, but will not constitute a protocol amendment. The IRB will be informed of any safety issues that require alteration of the safety monitoring scheme or amendment of the ICD.

Additional blood samples of approximately 0.5-1 mL using a micro sampling device (Tasso) will be collected, to provide approximately 0.25-0.5 mL serum into appropriately labeled tubes for measurement of ritlecitinib at selected timepoints as specified in the [SoA](#) Table. The “Tasso device” is a patient-centric sterile, disposable, integrated capillary blood collection device, including an at-home lancet assembly and a detachable reservoir, for the collection of blood by the user or caregiver in-home settings, without the need of a highly trained phlebotomist. This part of the study is designed to validate ritlecitinib PK concentrations in capillary blood collected using the Tasso device against PK samples collected from traditional venous blood samples. Findings from the validation may enable patient-centric blood sampling using this innovative device in future ritlecitinib clinical studies.

Blood samples from capillary blood vessels, collected using the Tasso device, should be timed as close as possible to the collection of ritlecitinib blood samples. The Tasso device should be attached to the upper arm. Details for collection and handling of the samples will be provided in the laboratory manual.

The blood samples collected using Tasso device will be used for internal exploratory purposes for comparing the ritlecitinib concentrations between venous and capillary blood. The results from this comparison will be documented in a separate internal bioanalytical report and will not be included in the CSR.

## **8.6. Genetics**

### **8.6.1. Specified Genetics**

Specified genetic analyses are not evaluated in this study.

### **8.6.2. Retained Research Samples for Genetics**

A 4-mL blood sample optimized for DNA isolation (Prep D1) will be collected according to the [SoA](#), as local regulations and IRBs/ECs allow.

Retained Research Samples may be used for research related to the study intervention(s). Genes and other analytes (eg, proteins, RNA, nondrug metabolites) may be studied using the retained samples.

See [Appendix 5](#) for information regarding genetic research. Details on processes for collection and shipment of these samples can be found in lab manual and other supporting documentation.

## **8.7. Biomarkers**

### **8.7.1. Retained Research Samples for Biomarkers**

These Retained Research Samples will be collected in this study:

A 10 mL blood sample (Prep B2) for serum will be collected as indicated in the [SoA](#) for retained research samples for biomarkers. Biomarker data may be generated to increase understanding of safety events associated with study intervention.

Retained Research Samples will be collected as local regulations and IRB/ECs allow according to the [SoA](#).

[figure not shown]
## **8.8. Immunogenicity Assessments**

Immunogenicity assessments are not included in this study.

## **8.9. Health Economics**

Health economics/medical resource utilization and health economics parameters are not evaluated in this study.

CCI

CCI

## 9. STATISTICAL CONSIDERATIONS

Detailed methodology for summary and statistical analyses of the data collected in this study is outlined here and further detailed in a SAP, which will be maintained by the sponsor. The SAP may modify what is outlined in the protocol where appropriate; however, any major modifications of the primary endpoint definitions or their analyses will also be reflected in a protocol amendment.

### 9.1. Statistical Hypotheses

No statistical hypothesis will be tested in this study.

### 9.2. Analysis Sets

For purposes of analysis, the following analysis sets are defined:

Population	Description
PK Concentration	The PK concentration population is defined as all participants randomized and treated who have at least 1 concentration in at least 1 treatment period.
PK Parameter	The PK parameter analysis population is defined as all participants randomized and treated who have at least 1 of the PK parameters of primary interest in at least 1 treatment period.
Safety	All participants randomly assigned to study intervention and who take at least 1 dose of study intervention. Participants will be analyzed according to the product they actually received.

### 9.3. Statistical Analyses

The SAP will be developed and finalized before database lock and will describe the participant populations to be included in the analyses, and procedures for accounting for missing, unused, and spurious data. This section is a summary of the planned statistical analyses of the primary and secondary endpoints.

#### 9.3.1. Efficacy Analyses

An efficacy analysis is not applicable to this study.

#### 9.3.2. Safety Analyses

AEs and safety laboratory data will be reviewed and summarized on an ongoing basis during the study to evaluate the safety of participants. Any clinical laboratory, ECG, BP, and pulse rate abnormalities of potential clinical concern will be described. Safety data will be presented in tabular and/or graphical format and summarized descriptively, where appropriate.

Medical history and physical examination information, as applicable, collected during the course of the study will be considered source data and will not be required to be reported, unless otherwise noted. However, any untoward findings identified on physical examinations conducted during the active collection period will be captured as AEs, if those findings meet the definition of an AE. Data collected at screening that are used for inclusion/exclusion criteria, such as laboratory data, ECGs, and vital signs, will be considered source data, and will not be required to be reported, unless otherwise noted. Demographic data collected at screening will be reported.

### 9.3.3. Pharmacokinetic Analyses

PK parameters following a single dose administration will be derived from the concentration-time profiles using noncompartmental methods as data permit. The various PK parameters to be assessed in this study, their definition, and method of determination are outlined in Table 4. In all cases, actual PK sampling times will be used in the derivation of PK parameters.

**Table 4. Definitions of PK Parameters**

Parameter	Definition	Method of Determination
AUC last	Area under the plasma concentration-time profile from time zero to the time of the last quantifiable concentration (C last )	Linear-log trapezoidal method
AUC inf	Area under the plasma concentration-time profile from time zero extrapolated to infinite time	AUC last + (C last /k el ) where C last is the predicted plasma concentration at the last quantifiable time point estimated from the log-linear regression analysis
C max	Maximum plasma concentration	Observed directly from the data
T max	Time for C max	Observed directly from the data as time of first occurrence
t 1/2	Terminal elimination half-life	Log e (2)/k el Only those data points judged to describe the terminal log-linear decline will be used in the regression.
CL/F	Apparent clearance after oral dose	Dose/AUC inf after oral dose
V z /F	Apparent volume of distribution after oral dose	Dose/(AUC inf *k el ) after oral dose

The plasma PK parameters in Table 4 will be summarized descriptively by treatment, as applicable, in accordance with Pfizer data standards. Plasma concentrations will be listed and summarized descriptively by nominal PK sampling time and treatment. Individual participant and median profiles of the plasma concentration-time data will be plotted by treatment using actual and nominal times, respectively. Median profiles will be presented on both linear-linear and log-linear scales.

Natural log transformed  $AUC_{inf}$  (if data permit),  $AUC_{last}$  and  $C_{max}$  will be analyzed using a mixed effects model with sequence, period and treatment as fixed effects and participant within sequence as a random effect. Estimates of the adjusted mean differences (Test-Reference) and corresponding 90% confidence intervals will be obtained from the model. The adjusted mean differences and 90% confidence intervals for the differences will be exponentiated to provide estimates of the ratio of adjusted geometric means (Test/Reference) and 90% confidence intervals for the ratios. Treatment A (intact BiCs) will be the Reference treatment and Treatments B, C, and D (BiCs sprinkled in strawberry jam, BiCs sprinkled in yoghurt, and BiCs sprinkled in applesauce) will be the Test treatments.

Natural log transformed  $AUC_{inf}$  (if data permit),  $AUC_{last}$  and  $C_{max}$  will be analyzed using a mixed effects model with sequence and treatment as fixed effects and participant within sequence as a random effect. Estimates of the adjusted mean differences (Test-Reference) and corresponding 90% confidence intervals will be obtained from the model. The adjusted mean differences and 90% confidence intervals for the differences will be exponentiated to provide estimates of the ratio of adjusted geometric means (Test/Reference) and 90% confidence intervals for the ratios. Treatment A (intact BiCs) will be the Reference treatment and Treatment E (intact BiCs given with high fat meal) will be the Test treatment.

CCI  
[REDACTED]

[REDACTED]

[REDACTED]

#### **9.4. Interim Analyses**

No interim analysis will be conducted for this study.

#### **9.5. Sample Size Determination**

A total of approximately 12 participants will be randomly assigned to study intervention such that approximately 3 participants will be enrolled to each of the 4 sequences. The following

table presents the widths of 90% confidence interval for different estimated effects for 12 participants:

Parameter	Estimated Effect (100*Test/Reference)	90%CI	CI Width
AUC inf	85%	77.75% to 92.92%	15.17%
	90%	82.33% to 98.39%	16.06%
	95%	86.9% to 103.85%	16.95%
	100%	91.47% to 109.32%	17.85%
	105%	96.05% to 114.79%	18.74%
	110%	100.62% to 120.25%	19.63%
	115%	105.20% to 125.72%	20.52%
C max	85%	71.56% to 100.97%	29.41%
	90%	75.77% to 106.91%	31.14%
	95%	79.98% to 112.84%	32.87%
	100%	84.19% to 118.78%	34.60%
	105%	88.40% to 124.72%	36.33%
	110%	92.60% to 130.66%	38.06%
	115%	96.81% to 136.60%	39.79%

These calculations are based on the estimates of within-participant standard deviations of 0.117 and 0.226 for  $\log_e AUC_{inf}$  and  $\log_e C_{max}$ , respectively, as obtained from studies B7981022, B7981029, and B7981030.

Participants who withdraw from the study or whose PK samples are determined to be non-analyzable may be replaced at the discretion of the investigator upon consultation with the sponsor.

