### Statistical Methods:

The following table presents the widths of 90% confidence interval for different estimated effects in 12 participants:

Parameter	Estimated Effect (100*Test/Reference)	90% CI	CI Width
AUC	85%	77.75% to 92.92%	15.17%
	90%	82.33% to 98.39%	16.06%
	95%	86.9% to 103.85%	16.95%
	100%	91.47% to 109.32%	17.85%
	105%	96.05% to 114.79%	18.74%
	110%	100.62% to 120.25%	19.63%
	115%	105.20% to 125.72%	20.52%
C max	85%	71.56% to 100.97%	29.41%
	90%	75.77% to 106.91%	31.14%
	95%	79.98% to 112.84%	32.87%
	100%	84.19% to 118.78%	34.60%
	105%	88.40% to 124.72%	36.33%
	110%	92.60% to 130.66%	38.06%
	115%	96.81% to 136.60%	39.79%

These calculations are based on the estimates of within-participants standard deviations of 0.117 and 0.226 for logeAUCinf and logeCmax, respectively, as obtained from studies B7981022, B7981029, and B7981030.

Natural log transformed AUCinf (if data permit), AUClast and Cmax will be analyzed using a mixed effects model with sequence, period and treatment as fixed effects and participant within sequence as a random effect. Estimates of the adjusted mean differences (Test-Reference) and corresponding 90% confidence intervals will be obtained from the model. The adjusted mean differences and 90% confidence intervals for the differences will be exponentiated to provide estimates of the ratio of adjusted geometric means (Test/Reference) and 90% confidence intervals for the ratios. Treatment A (pediatric capsules, fasted) will be the Reference treatment and Treatments B-D (pediatric capsules sprinkled in strawberry jam, pediatric capsules sprinkled in yoghurt, and pediatric capsules sprinkled in applesauce) will be the Test treatments.

Natural log transformed AUCinf (if data permit), AUClast and Cmax will be analyzed using a mixed effects model with sequence and treatment as fixed effects and participant within sequence as a random effect. Estimates of the adjusted mean differences (Test-Reference) and corresponding 90% confidence intervals will be obtained from the model. The adjusted mean differences and 90% confidence intervals for the differences will be exponentiated to

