#### **For the primary objective – relative BA:**

```
proc mixed data=tab.pk;
  class seq period trt participant;
  model l&var=seq period trt/ ddfm=KR;
  random participant(seq) /subject=participant(seq);
  lsmeans trt;
  estimate 'B vs A' trt -1 1 0 0 0 /cl alpha=0.1;
  estimate 'C vs A' trt -1 0 1 0 0 /cl alpha=0.1;
  estimate 'D vs A' trt -1 0 0 1 0 /cl alpha=0.1;

  ods 'Estimates' out=est&var;
  ods 'lsmeans' out=ls&var;
  ods 'covparms' out=cov&var;
  ods 'tests3' out=tst&var;
run;
```

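### Are the 90% CI widths that support n=12 wrong, given that the stated SDs produce intervals about 10% narrower?

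*Protocol*

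**What the plan says.** Protocol Section 9.5 states: "A total of approximately 12 participants will be randomly assigned to study intervention such that approximately 3 participants will be enrolled to each of the" four sequences. It then says that the "table presents the widths of 90% confidence interval for different estimated effects for 12 participants", and prints seven rows each for AUCinf and Cmax, at estimated ratios from 85% to 115%. At a ratio of 100% the AUCinf interval is "91.47% to 109.32"%, width 17.85, and the Cmax interval is 84.19% to 118.78%, width 34.60. The stated basis is: "These calculations are based on the estimates of within-participant standard deviations of 0.117 and 0.226", with three earlier studies named as the source.

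The Synopsis, under Statistical Methods, prints the same 14 rows with the same description: "The following table presents the widths of 90% confidence interval for different estimated effects in 12 participants". Neither place gives degrees of freedom, a probability attached to the width, or the treatment comparison that the table covers. The SAP has no sample size section.

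Section 9.1 says: "No statistical hypothesis will be tested in this study". The table is therefore the only quantitative support for 12 participants.

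**The concern.** A reader who takes the table at its word will compute an ordinary 90% CI from n=12 and the two SDs, and will match none of the printed figures. The gap is too large for rounding. An ordinary interval at 30 degrees of freedom would need SDs of about 0.129 and 0.248 to give the printed widths, and no rounding of 0.117 and 0.226 reaches those values.

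The natural suspicion is that a wrong SD, a wrong sample size or a faulty formula went into the only calculation behind n=12. If so, the expected precision of both primary endpoints would be misstated.

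**Working it through.** **Inputs.** From Protocol Section 9.5: n = 12, a 90% two-sided interval, and SD = 0.117 (log AUCinf) and 0.226 (log Cmax). From Section 9.3.3: one model for Treatments A to D with sequence, period and treatment fixed and participant within sequence random. With complete data the error degrees of freedom are 48 observations − 12 participants − 3 periods − 3 treatments = 30. The design matrix of the four sequences gives a variance of 2·SD²/12 for each of B, C and D versus A.

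**Ordinary 90% CI.** Log half-width h = t(0.95, df) × SD × √(2/12), with t(0.95, 30) = 1.6973. At a ratio of 100%:

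- AUCinf: h = 1.6973 × 0.117 × 0.40825 = 0.0811, so 92.21 to 108.44, width 16.23.
- Cmax: h = 1.6973 × 0.226 × 0.40825 = 0.1566, so 85.50 to 116.95, width 31.45.

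The printed widths are 17.85 / 16.23 = 1.10 and 34.60 / 31.45 = 1.10 times these. The ratio is 1.10 in all 14 rows. A constant factor points to one extra multiplier applied throughout, not to scattered slips.

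**Recovering the multiplier.** Dividing each printed log half-width by SD × √(2/12) gives 1.865 to 1.866 in every row. For AUCinf at 100%: ½·ln(109.32/91.47) = 0.0891, and 0.0891 / (0.117 × 0.40825) = 1.866.

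**Reproducing the plan's figures.** The estimated SD varies from trial to trial. It stays below SD × √(χ²(0.80, df)/df) with 80% probability. At 30 df, √(36.25/30) = 1.0992, and 1.6973 × 1.0992 = 1.8657. At a ratio of 100%:

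- AUCinf: h = 1.8657 × 0.117 × 0.40825 = 0.0891, so 91.47 to 109.32, width 17.85, as printed.
- Cmax: h = 1.8657 × 0.226 × 0.40825 = 0.1721, so 84.19 to 118.78, width 34.60, as printed.

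Over the whole table this reproduces 28 of 28 limits and 14 of 14 widths to two decimals (largest deviation 0.005).

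**Other readings tried.** The widths are for AUCinf and Cmax at 100%; the last column counts matches to two decimals.

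| Reading | Widths | Printed values matched |
|---|---|---|
| Ordinary CI, A–D, 30 df | 16.23, 31.45 | 0 of 42 |
| Ordinary CI, Period 5 included, 41 df | 16.09, 31.18 | 0 of 28 limits |
| Ordinary CI, one treatment pair with period, 8 df | 17.79, 34.48 | 0 of 42 |
| 80% probability, 41 df | 17.48, 33.89 | 0 of 42 |
| 80% probability, 30 df | 17.85, 34.60 | 42 of 42 |

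An ordinary interval with 10 participants and 27 df matches 34 of 42, but it contradicts the stated 12. With n fixed at 12, a search over 5 to 60 df and a range of probabilities found only 80% at 30 df within 0.005 of every limit and width.

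**Food effect (E versus A).** This comparison has its own model, a "mixed effects model with sequence and treatment as fixed effects and participant within sequence as a random effect", with no period term. If only A and E data are used (an assumption; 24 − 12 − 1 = 11 df), the ordinary widths are 17.18 and 33.29, still below print. On the 80% basis, t(0.95, 11) × √(14.63/11) = 1.7959 × 1.1533 = 2.0712, which gives 19.82 and 38.45, above print.

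**The case for a change.** The case for asking for a change is that a 90% CI and a width not exceeded with 80% probability are different quantities, and the table is labelled as the first while apparently showing the second. The table carries the whole sample size argument, so a reader should be able to reproduce it. Food effect is also a primary objective, and the table does not say whether it covers E versus A. One sentence would settle both points.

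The facts in that case stand. The label is incomplete, and the 80% basis is an inference from a numerical match that only the sponsor can confirm. It is also true that calling the printed figures cautious holds for B, C and D versus A but cannot be extended without qualification to E versus A on the same 80% basis.

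What does not stand is the step from there to a needed change. Section 9.5 says the calculations are based on the two SDs; it does not say they are the only inputs. Added wording would record how existing figures were obtained without altering any of them. Replacing the rows with ordinary widths would discard figures that the evidence suggests are right and are the more careful choice for planning.

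The relative bioavailability code in SAP Appendix 1 writes five-level contrasts ("estimate 'B vs A' trt -1 1 0 0 0 /cl alpha=0.1"), which raises the question of whether Period 5 enters that model. That is a separate matter from how this table was built, and 41 df does not explain the printed figures.

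**Conclusion.** The concern does not call for a change. The printed widths are about 10% wider than ordinary 90% CIs from the stated inputs, but they fit one coherent calculation exactly, so this is an unstated assumption and very probably not an arithmetic error. For B, C and D versus A the omission errs on the safe side: the ordinary widths at a ratio of 100% are 16.23 and 31.45 against 17.85 and 34.60 printed.

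For E versus A the table is a looser guide. Under the assumed 11 df the ordinary widths (17.18 and 33.29) still fall below print, but the 80%-probability widths (19.82 and 38.45) do not. Nothing in the plan turns on that difference, since no hypothesis is tested and no acceptance limit is applied. The reported intervals will come from the fitted models and the study's own variance estimate, so the planning table does not enter the results.

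This rests on complete data from 12 participants, on 30 df for the A to D model, and on the inferred 80% basis. Even if that inference were wrong, the ordinary intervals for B, C and D versus A would still be narrower than printed, and the case for 12 participants would be no weaker.
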